15.2 Sample Size

Based on our preliminary studies, we anticipate that 10% of all potential participants will not be eligible and/or willing to participant; and that 10% of the eligible/willing participants will be lost to follow-up. Therefore, we will recruit a total of n=50 individuals for the current study. This is a feasible sample size for the research team to recruit and enroll in the current study. Power calculations were based on the anticipated total sample size (n=40) that will be available for complete analysis.

We will develop separate mixed-effects general linear models for each of the continuous outcomes. From the anticipated sample size (n=40) the study has 86% power to detect a 10% main effect of each treatment for each outcome, our anticipated effect size given preliminary studies. When using count data the study has 94% power to detect a 10% decrease in the rate of outcomes (coughing, wheezing, etc.), our anticipated change in the rate. Using the dichotomized version of some outcomes, this study has 80% power to detect on odds ratio of 1.32 with a two sided $\alpha=0.05$ (n=40). Therefore, we have more than sufficient numbers of participants in each comparison group.

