Adult and Adolescent Patients 12 Years of Age and Older: Efficacy was evaluated in 669 asthma patients, 12 to 78 years of age, including 88 patients 12-17 years of age and 581 patients 18 years and older. Mean FEV1 at screening was 2.44 L and mean FEV1 at baseline was 2.72 L following the 2-week run-in period. Patients were randomized to AEROSPAN Inhalation Aerosol 80 mcg, 160 mcg or 320 mcg twice daily, flunisolide CFC inhalation aerosol 250 mcg, 500 mcg, or 1000 mcg twice daily, or placebo. Change from baseline in percent predicted FEV1 over 12 weeks treatment demonstrated that placebo patients deteriorated 4.3% from baseline after 12 weeks of treatment, whereas patients treated with AEROSPAN Inhalation Aerosol 160 mcg or 320 mcg twice daily maintained FEV1 over the course of the study. Results for the comparison to placebo were statistically significant for the 160 and 320 mcg twice daily AEROSPAN Inhalation Aerosol doses (see Figure 1), but not for the 80 mcg dose. Secondary endpoints of AM peak expiratory flow rate, AM and PM asthma symptoms, nocturnal awakenings requiring a β 2 agonist, and as needed use of inhaled β 2 agonists showed differences from baseline favoring AEROSPAN Inhalation Aerosol over placebo. AEROSPAN Inhalation Aerosol and flunisolide CFC inhalation aerosol gave comparable results.

Pediatric Patients 4 to 11 Years of Age: The trial enrolled 583 asthma patients, 4 to 11 years of age, although the primary efficacy parameter was evaluated only in the population of 513 patients 6 to 11 years of age. In these patients, the mean FEV1 at screening was 81.2% predicted, and the mean FEV1 at baseline following a two week run-in period was 87.5% predicted. Patients were randomized to

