AEROSPAN Inhalation Aerosol 80 mcg or 160 mcg twice daily, flunisolide CFC inhalation aerosol 250 mcg or 500 mcg twice daily, or placebo. Change from baseline in percent predicted FEV1 over 12 weeks in patients 6 years of age and older demonstrated that placebo patients deteriorated 4.0% from baseline after 12 weeks of treatment; whereas patients treated with AEROSPAN Inhalation Aerosol 80 mcg or 160 mcg twice daily maintained FEV1 over the course of the study. Results for the comparison to placebo were statistically significant for the 80 mcg and 160 mcg doses of AEROSPAN Inhalation Aerosol, but there was no added benefit for the 160 mcg BID dose over the 80 mcg BID dose (see Figure 2). AEROSPAN Inhalation Aerosol and flunisolide CFC inhalation aerosol gave comparable results in patients 6 years of age and older.

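### The 86% power figure names no between-dose difference, scale or SD, so it does not support the 80 versus 160 mcg comparison, least of all for FEV1

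*Combined protocol and SAP*

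**What the plan says.** The synopsis gives the objective as finding out whether response differs by dose. Its primary endpoint compares change from baseline between the one-inhalation and two-inhalation groups. FEV1 is a primary variable there and in section 4.2.

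Section 15.2, repeated in the synopsis, sets the numbers: "Therefore, we will recruit a total of n=50 individuals for the current study", and "Power calculations were based on the anticipated total sample size (n=40) that will be available for complete analysis". For continuous outcomes it says "the study has 86% power to detect a 10% main effect of each treatment for each outcome, our anticipated effect size given preliminary studies". It ends by calling the numbers in each comparison group more than enough. The preliminary studies are not described, and no SD, within-patient correlation or measurement scale appears anywhere.

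Section 15.1 defines the primary endpoint as change over time from baseline to six weeks. It plans paired t-tests first, then mixed models.

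Section 1.6 summarises the earlier 12-week trials in percent predicted FEV1:
- **Ages 6-11 (513 children):** "placebo patients deteriorated 4.0% from baseline after 12 weeks of treatment", both 80 and 160 mcg twice daily maintained FEV1, and "there was no added benefit for the 160 mcg BID dose over the 80 mcg BID dose".
- **Ages 12 and over:** "placebo patients deteriorated 4.3% from baseline after 12 weeks of treatment", while 160 and 320 mcg maintained FEV1. Those two doses differed significantly from placebo; 80 mcg did not.

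**The concern.** A power statement supports a trial only if it refers to the comparison the trial is meant to make. Here the phrase about a main effect of each treatment can be read as each arm's own improvement or as the difference between doses. The first reading gives no power for the objective. The second asks for an effect on FEV1 that the plan's own background does not lead one to expect, at least in the younger children.

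What is at stake is interpretation. With the groups described as amply sized, a non-significant FEV1 comparison could be taken as evidence that the doses are equal, when the confidence interval may still contain differences as large as those in section 1.6.

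**Working it through.** **Inputs from the documents.** 50 recruited and 40 analysed (15.2); equal allocation, so 20 per arm (7.2); stated power 86% for 10% (15.2); percent predicted FEV1 results (1.6). Two-sided 0.05 is stated only in the 15.2 sentence on dichotomised outcomes; I assume it applies here too.

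**The plan's own figures.** The 40 reproduces from the stated losses, "10% of all potential participants will not be eligible and/or willing to participant; and that 10% of the eligible/willing participants will be lost to follow-up": 50 × 0.9 × 0.9 = 40.5. The 86% cannot be reproduced forwards without an SD. It can only be solved backwards for the SD it implies.

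**Formulas.** Power is from the noncentral t distribution.
- Between arms: noncentrality = (difference/SD) × √(20/2), 38 df.
- Paired, n patients: noncentrality = (change/SD) × √n, n − 1 df.
- 95% CI half-width between arms: 2.024 × √(2/20) = 0.640 SD.

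SD means the SD of change, assumed equal in both arms. I first read 10% as 10 points of percent predicted; this is an assumption.

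**What 20 per arm delivers on any continuous outcome.** 80% power needs a between-dose difference of 0.909 SD; 86% needs 0.987 SD.

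**Reading A: 10% is a within-arm change.** The implied SD is then used for the between-dose test at 20 per arm.

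| Paired test behind the 86% | Implied SD | Between-dose power, 10 points | Between-dose power, 4 points |
|---|---|---|---|
| one arm, n = 20 | 13.9 | 60% | 14% |
| both arms pooled, n = 40 | 20.3 | 33% | 9% |

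**Reading B: 10% is a between-dose difference.** Implied SD = 10/0.987 = 10.1 points. For comparison, the active-versus-placebo contrast at ages 6-11 in section 1.6 is about 4 points (a fall of 4.0 against no change).

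| True dose difference on FEV1 | Power at SD 10.1 |
|---|---|
| 10 points | 86% |
| 4 points | 23% |
| 2 points | 9% |
| 0 | 5% (the alpha level) |

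The CI half-width at that SD is 0.640 × 10.1 = 6.5 points.

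**Sensitivity to scale.** If 10% is relative, it is 8.1 to 8.75 points on the mean FEV1 values of 81.2 and 87.5% predicted in section 1.6. The implied SDs are then 8.2 to 8.9, and power for 4 points is 32% to 28%.

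**Sensitivity to SD.** Power for a 4-point dose difference at assumed SDs of 5, 8, 10, 15 and 20 is 69%, 34%, 23%, 13% and 9%.

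**The case against.** The best defence is that section 1.6 is a poor guide to this trial, and several parts of it stand.

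- **Age.** The finding of no added benefit is for ages 6-11. This trial enrols to 18 (sections 4.1 and 5.2.1) or 21 (synopsis). At 12 and over, 160 mcg but not 80 mcg differed significantly from placebo. That is not a direct test of one dose against the other, but it points towards a possible difference. A reader might infer that the background rules out a dose effect in this population; it does not.
- **Design.** All patients in the earlier trials had two weeks of active flunisolide before randomisation, so about 4 points is a maintenance contrast over 12 weeks. A reader might take it as the drug's entire effect. The documents do not support that: in the paediatric trial mean FEV1 rose from 81.2 to 87.5, or 6.3 points, from screening to the end of the uncontrolled run-in. Patients here start off inhaled steroids and could improve more. That makes a 10% change within each arm more plausible, but gives no support for a 10% difference between arms.
- **Outcomes.** The dose hypothesis in section 1 lists small-airway measures and omits FEV1, and section 1.7 notes that the pivotal trials looked only at FEV1. It would be tempting to call 10% implausible throughout, but the documents contain no dose data on FEF25-75 or oscillometry. There the 10% is undocumented, not contradicted.
- **Equal-dose claims.** The plan nowhere says it will read a null result as equal doses. The fix is a safeguard against that reading.

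None of this supplies the missing contrast, scale or SD, and the claim expressly covers every outcome, FEV1 included.

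**Conclusion.** The point holds: the 86% is not supported for the dose contrast under either reading. Read within arms, it answers a different question, and between-dose power for the same 10 points is about 60% or 33%. Read between arms, it presumes an FEV1 difference that section 1.6 does not lead one to expect at ages 6-11; power for 4 points is about 23%, or 28-32% if the 10% is relative.

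These figures rest on back-solved SDs, two-sided 0.05 and a simple comparison of change. Over assumed SDs of 5 to 20, power for 4 points runs from 69% to 9%, so it would go too far to say that the trial could neither detect nor exclude such a difference: below an SD of 6.25 (4/0.64) the CI half-width is under 4 points. The conflict with the background is limited to FEV1. The lack of a defined contrast, scale and SD affects every continuous outcome.

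**What to change.** In section 15.2 and the matching synopsis text:

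1. Replace the claim of 86% power for each outcome, and the closing statement on numbers, with what 20 per arm delivers for the between-dose difference in change on any continuous outcome: 80% power at 0.91 SD, 86% at 0.99 SD, and a 95% CI half-width of 0.64 SD, two-sided 0.05. Removing FEV1 alone would leave the same undefined figure standing for FEF25-75 and oscillometry.
2. Wherever a 10% effect is kept, say that it is a between-dose difference, and give its scale, the SD of change and the source of both. Cite the section 1.6 FEV1 results for both age groups beside it.
3. State that the dose difference will be reported with its confidence interval, and that a non-significant FEV1 comparison will not be presented as showing equal doses.

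This is a wording change and needs no extra patients. The cost is a less favourable stated figure.

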We will develop separate mixed-effects general linear models for each of the continuous outcomes. From the anticipated sample size (n=40) the study has 86% power to detect a 10% main effect of each treatment for each outcome, our anticipated effect size given preliminary studies. When using count data the study has 94% power to detect a 10% decrease in the rate of outcomes (coughing, wheezing, etc.), our anticipated change in the rate. Using the dichotomized version of some outcomes, this study has 80% power to detect an odds ratio of 1.32 with a two sided $\alpha=0.05$ (n=40). Therefore, we have more than sufficient numbers of participants in each comparison group.

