4.3 Secondary Efficacy Endpoints

The number of protocol-defined asthma exacerbations requiring treatment with oral steroids between the two groups will be monitored. We will also track frequency of albuterol use for acute symptoms, number of emergency room visits and hospital admissions for acute asthma exacerbations between the two groups.

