7.2 Test Formulation

Subjects will be randomized equally to receive HFA Flunisolide 80mcg (AEROSPAN Inhalation Aerosol, MEDA Pharmaceuticals, Somerset, NJ) 1 inhalation BID or HFA Flunisolide 80mcg 2 inhalations BID. All inhalations will be delivered using the built-in spacer device without any other attached devices, holding chambers, spacers, or masks. Patients will be fully instructed on how to administer the medication exactly according to manufacturer's specifications as discussed in the package insert.

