15.1 Analysis of Physiologic Effects (Lung Function)

The primary goal of the current study is to determine the effects of Aerospan on lung function in children with small airway obstruction. Participants recruited into this randomized parallel group study will be randomly assigned to either receive (1) 80 mcg of Aerospan twice a day or (2) 160 mcg of Aerospan twice a day, during the six-week study period. Outcomes will be measured at baseline and at six-week follow-up as described above.

First we will start with straightforward tests for differences among the two groups to test if our randomization scheme was successful. Analysis of Variance (ANOVA) techniques will be used to test for difference among continuous variables, while Kruskal-Wallis, Fischer's Exact Tests and Wilcoxon methods will be used to test for differences among categorical variables.

The primary endpoint will be changes in outcomes, over time, from baseline to six-week follow-up. The change in scores from baseline to six-week follow-up will initially be compared using paired t-tests and Chi-squared tests for trend. Repeated measurements will be analyzed using generalized linear mixed-effects regression modeling (GLMM) techniques. For continuous outcomes (e.g., FEV1, FEF 25-75%, Fres, X5, AX, R5-R20.) the identity link function and normal distribution will be used. For count data (e.g., use of Beta-agonists, episodes of

coughing, episodes of wheezing, etc.) the log link function and the Poisson distribution will be used. If we dichotomize outcomes (e.g., a Beta-agonist was used, coughing occurred, etc.) the logit link function and Bernoulli distribution will be used. Statistical analyses will be performed using SAS® Version 9.3 (SAS Institute Inc., Cary, NC).

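### The 94% power stated for a 10% lower count rate cannot be reproduced; it implies about 118 events per child with no extra-Poisson variation, which the rare secondary counts cannot supply

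*Combined protocol and SAP*

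**What the plan says.** Section 15.2 (Sample Size) gives three power statements. The one for counts reads "When using count data the study has 94% power to detect a 10% decrease in the rate of outcomes (coughing, wheezing, etc". The synopsis, under the rationale for the number of subjects, has the same sentence. Both paragraphs end by concluding that each comparison group is more than large enough.

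The sample behind the figure is given as "Power calculations were based on the anticipated total sample size (n=40"). Section 7.2 fixes the allocation: "Subjects will be randomized equally to receive HFA Flunisolide 80mcg" at one or two inhalations twice daily. Section 15.1 names beta-agonist use, coughing and wheezing as examples of counts and says that for such data "the log link function and the Poisson distribution will be used". Section 4.3 lists oral-steroid exacerbations as a secondary endpoint and adds: "We will also track frequency of albuterol use for acute symptoms, number of emergency room visits and hospital admissions". Section 1 also lists frequency of coughing and wheezing as secondary. Section 7.4 says that albuterol use can be read from the inhaler counter.

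No section gives an expected number of events per child for any count, a measure of between-child variation, or the contrast to which the 94% refers. Two-sided 0.05 appears only in the odds-ratio sentence.

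**The concern.** A power figure for a rate ratio has no meaning without an event rate. A 10% reduction is small on the log scale, and 40 children followed for six weeks give enough information to detect it only if each child contributes many events and the children have nearly the same underlying rate. Several of the counts in section 4.3 are events that most children would not be expected to have even once in six weeks.

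The figure also helps to support the closing claim of ample numbers in each group. A reader who relies on it could take a non-significant comparison of exacerbations or emergency visits as evidence that the doses do not differ, when the trial could hardly have shown a 10% difference in those events.

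**Working it through.** **Inputs**
- Power 94%, rate ratio 0.90, 40 children in total (section 15.2).
- Equal allocation (section 7.2), so 20 per dose. The 40 follows from the stated losses: 50 × 0.9 × 0.9 = 40.5.
- Two-sided 0.05: stated for the odds ratio only, assumed here for counts too.
- Poisson model with log link (section 15.1); 42 days of treatment.
- Event rate and dispersion: not given. The values below are assumptions, shown as ranges.

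**Attempt to reproduce the 94%**

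It cannot be calculated forwards, because the rate is missing. It can be solved for the rate that would produce it. With μ events per child in the higher-rate arm, the variance of the log rate ratio is (1/μ + 1/(0.9μ))/20.

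- Required standard error: |ln 0.9| / (1.960 + 1.555) = 0.1054 / 3.515 = 0.02998.
- μ = (1 + 1/0.9) / (20 × 0.02998²) = 117.5 events per child.
- That is 117.5/42 = 2.8 per day, or about 2,350 events in the higher-rate arm.

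A simulation of 400,000 Poisson trials at 118 events per child gave 94.2% power.

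**Other readings, events per child needed for 94%**

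| Reading | Events per child |
|---|---|
| 20 vs 20, one-sided | 97 |
| 22 vs 22, two-sided | 107 |
| 25 vs 25 (no losses), two-sided | 94 |
| Before vs after in all 40, two-sided | 59 per period |
| Difference in differences, 20 vs 20, two-sided | 229 per period |

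Taking n=40 as 40 per group also gives 59, but section 15.2 calls it the total.

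**Power for the dose comparison, pure Poisson**

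Power = Φ(0.1054/SE − 1.960), with SE² = (1/μ + 1/(0.9μ))/20. Rejections in the wrong direction are not counted.

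| Assumed events per child in six weeks | Power |
|---|---|
| 0.5 | 4% |
| 1 | 5% |
| 2 | 7% |
| 10 | 18% |
| 42 (one a day) | 56% |
| 84 (two a day) | 84% |
| 118 | 94% |

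**Between-child variation**

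Let k be the squared coefficient of variation (CV) of the children's underlying rates. Then SE² = (1/μ + 1/(0.9μ) + 2k)/20. At 118 events:
- k = 0.01: SE = 0.0435, power 68%.
- k = 0.05: SE = 0.0768, power 28%.
- k = 0.25: SE = 0.1609, power 10%.

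As μ grows without limit, SE² tends to 2k/20. For 94% this must not exceed 0.02998², so k ≤ 0.0090, a CV of at most √0.0090 = 9.5%. Above that, no event rate gives 94% in a comparison between arms with one count per child.

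**The case against.** The strongest reply is that the power sentence names coughing and wheezing, not admissions, and that section 15.1 adds beta-agonist use. The documents give no rate for any of these. Albuterol is read from a counter, so the unit is actuations, and 2.8 a day is possible for some children with mild to moderate asthma. This stands. A reader might infer that no count in the trial could reach the required rate; the documents do not show that. Nor does the exclusion of acute wheezing in section 5.2.2 settle it, since it applies to the screening and baseline visits and does not bound the next six weeks of albuterol use.

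Secondly, the contrast is not stated. Section 15.1 speaks of change over time and paired tests, and on a before-and-after reading in all 40 children the requirement halves to about 59 per period. This is a fair reason to attach conditions to the 118. But that reading does not compare doses, which is the trial's stated purpose, and it needs a pre-treatment count. The study albuterol inhaler is first dispensed at Visit 2 (section 9.2), so its counter provides no baseline period.

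Thirdly, the between-child variance is an assumption. That is so, and the range is shown for that reason. A reader might also take power to be about 10% at every event rate when k = 0.25. It is not: it is about 5% at one event and about 8% at 10, and 10% is the ceiling.

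Finally, these outcomes are secondary, and no section says that a non-significant count result will be read as no dose difference. Both points stand and limit the weight of the concern.

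**Conclusion.** The 94% is not reproducible from the plan. As a between-dose claim it requires about 118 events per child in six weeks and virtually no variation between children beyond Poisson. This rests on 20 versus 20, a rate ratio of 0.90 and two-sided 0.05; the other readings move the requirement but none makes it small, and the most favourable two-sided one still needs about 59 per period.

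For oral-steroid exacerbations, emergency visits and admissions, the stated power is out of reach: at most about 7% at assumed rates of 0 to 2 per child. For albuterol actuations, cough and wheeze the answer depends on a rate and a dispersion that the plan does not give. It would be tempting to say that the trial had almost no chance of detecting a difference in any count. That does not hold for a frequent count with low dispersion, where power is 56% at one event a day and 84% at two. What can be said is that 94% cannot be reached at any rate once the between-child CV exceeds about 9.5%.

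This should be corrected, but it concerns secondary outcomes only. The primary lung-function comparison is not touched by it.

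**What to change.** In section 15.2 and in the synopsis, withdraw the 94% sentence. For each count that is kept, state the between-dose contrast, alpha, a range of expected events per child over six weeks and a range of between-child variance, and give the power or the detectable rate ratio across those ranges. The two power tables above show the form. Limit the closing statement about adequate numbers so that it does not cover count outcomes. If the sponsor has preliminary rates that support a higher figure, this is the place to cite them.

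Section 15 foresees a separate, detailed SAP that may modify the plan, so the same text can be carried there. Labelling the count comparisons as descriptive, with estimates and confidence intervals, is an option but does not follow from the arithmetic.

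The cost is wording in two places and a less favourable stated figure. The sample size, the data collected and the primary analysis do not change.

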1.8 Secondary endpoints

Secondary endpoints include asthma symptom control as defined by the standardized asthma control test (ACT). We will also examine the number of corticosteroid courses, ED visits, and admissions patients in each group has over the study period.

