8.2.3 Concomitant Medications and Pulmonary Exacerbations

All concomitant medication and concurrent therapies will be documented at the Baseline visit. Dose, route, unit frequency of administration, and indication for administration and dates of medication will be captured. An interim history and chart review will be performed at each subsequent study visit, including interim hospitalizations for respiratory symptoms and interim courses of steroids (date, route, indication).

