9.2 Visit 2 (Baseline) (Day 0)

Subjects who meet eligibility criteria at Visit 1 will be scheduled to return for Visit 2 no sooner than the next day but no later than 56 days following the Screening Visit. The following procedures will be completed:

1. Obtain standardized asthma control score from parent/legal guardian
2. Review current health status/medical history
3. Review concomitant medications
4. Obtain vital signs (temperature, heart rate, respiratory rate and blood pressure)

5. Measure oximetry
6. Measure height and weight
7. Perform abbreviated physical examination (Investigator)
8. Have patient perform IOS pre-bronchodilator
9. Have patient perform spirometry pre-bronchodilator
10. Have patient perform IOS post-bronchodilator
11. Have patient perform spirometry post-bronchodilator

If the subject meets all eligibility:

12. Randomize to flunisolide HFA 80mcg 1 puff BID or flunisolide HFA 80mcg 2 puffs BID
13. Dispense Study Drug and albuterol sulfate with holding chamber.
14. Review instructions for Study Drug administration
15. Schedule subject for Visit 3 (Week 6 ± 1 week)

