16 DATA COLLECTION, RETENTION AND MONITORING

16.1 Data collection

Data that will be collected during the study include: enrollment and randomization information, spirometry/IOS data, other subject data collected during the study visit, and asthma controls scores. This data will be kept in a secure, locked filing cabinet in the pediatric pulmonary clinic office.

An electronic database of data will be created using Microsoft Excel. This database will be encrypted, password protected, and stored exclusively on a password protected computer in the pediatric pulmonary clinic.

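### Cough and wheeze counts are modelled and given 94% power although no listed procedure records them, while the asthma control score that is collected is missing from 4.3 and unnamed in section 15

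*Combined protocol and SAP*

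**What the plan says.** **Cough and wheeze.** The background (section 1) counts their frequency among the secondary outcomes. Section 15.1 and the synopsis statistics row give episodes of each as examples of count data for a Poisson model with log link, and give the occurrence of coughing as an example of a dichotomised outcome. Section 15.2, repeated in the synopsis, then claims "94% power to detect a 10% decrease in the rate of outcomes (coughing, wheezing, etc". The sample behind that figure is stated: "Power calculations were based on the anticipated total sample size (n=40) that will be available for complete analysis".

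**What is collected.** Section 7.4 takes albuterol use from the inhaler counter. Section 8.2.3 provides an interim history and chart review, "including interim hospitalizations for respiratory symptoms and interim courses of steroids". Visits 2 and 3 both open with the same item: "Obtain standardized asthma control score from parent/legal guardian". Section 16.1 lists enrolment and lung function data, "other subject data collected during the study visit, and asthma controls scores".

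**Asthma control score.** Section 1.8 states: "Secondary endpoints include asthma symptom control as defined by the standardized asthma control test (ACT". The synopsis row on efficacy evaluations says that control scores will be compared between the two dose groups. Section 4.3 does not mention the score. It begins "The number of protocol-defined asthma exacerbations requiring treatment with oral steroids between the two groups will be monitored" and adds albuterol use, emergency visits and admissions. The synopsis secondary-endpoint row has exacerbations only.

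**The concern.** There are two separate gaps.

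The first is in data collection. A site that follows the visit lists exactly will finish with no cough or wheeze counts, so the Poisson model, the dichotomised version and the power claim have nothing to act on. A statistical analysis plan written later cannot supply observations that were never made. The 94% also feeds the closing statement of 15.2 that the numbers are more than sufficient, so a reader may credit the trial with sensitivity to symptom change that nothing supports.

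The second is in specification. The control score is scheduled at both baseline and Week 6, yet the section that defines the secondary endpoints omits it and the statistical section does not name it. Section 1, section 1.8, section 4.3 and the synopsis row give four different secondary lists. The trial is open label, and section 15 requires the detailed analysis plan only before the data are analysed. The choice among lists could therefore be made once results by arm can be seen.

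**Working it through.** **Is there a source for each clinical outcome?**

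| Outcome | Where named as an outcome | Stated source |
|---|---|---|
| Cough and wheeze episodes | Sections 1, 15.1, 15.2; synopsis statistics rows | None found |
| Albuterol use | Sections 1, 4.3, 15.1 | Counter, 7.4 |
| Steroid courses | Sections 1, 1.8, 4.3 (as exacerbations treated with oral steroids) | 8.2.3 |
| Hospitalizations | Sections 1, 1.8, 4.3 | 8.2.3 |
| Asthma control score | Section 1.8; synopsis efficacy row | Visits 2 and 3; 16.1 |

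The nearest Visit 3 item to a symptom record is a general review of health status and adverse events. It has no episode count, diary or recall period.

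**Can the 94% be reproduced?** Inputs from the documents:
- 40 analysed (50 × 0.9 × 0.9 = 40.5), equal randomisation (7.2), so 20 per arm
- rate ratio 0.90, from "10% decrease in the rate of outcomes (coughing, wheezing, etc.), our anticipated change in the rate"
- two-sided 0.05, which 15.2 states only for the odds ratio and which is assumed here for counts
- six weeks = 42 days

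The documents give no baseline rate and no overdispersion, so the figure cannot be reproduced. What can be found is the rate it would require.

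Let L be the mean count per child in the lower-dose arm, with n = 20 per arm. For a Wald test on the log rate ratio under a pure Poisson model:

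Power = Φ( |ln 0.9| / √(1/(nL) + 1/(0.9nL)) − 1.96 )

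Solving for 94% power:

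L = (1 + 1/0.9)/20 × ((1.960 + 1.555)/0.10536)² ≈ 117 episodes per child, or 117/42 = 2.8 a day, about 4,460 episodes in total.

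Variants of the requirement:
- one-sided test: about 97 per child (2.3 a day)
- all 50 analysed, 25 per arm: 94 per child (2.2 a day)
- 40 children compared before and after, with no between-child variance: about 59 per child per period (1.4 a day). This does not compare the doses, and it needs a baseline count that is not scheduled either.

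Power at assumed rates (20 per arm, two-sided 0.05), with the variance multiplied by an overdispersion factor φ:

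| Episodes per child in 6 weeks | φ = 1 | φ = 2 | φ = 4 |
|---|---|---|---|
| 10 | 17.5% | 10.8% | 7.4% |
| 20 | 30.5% | 17.5% | 10.8% |
| 42 (one a day) | 55.6% | 31.8% | 18.2% |
| 84 (two a day) | 84.4% | 55.6% | 31.8% |
| 112 | 92.9% | 68.0% | 40.4% |

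If children differ in their underlying rates, more episodes do not rescue the comparison. With negative binomial dispersion k, the standard error of the unadjusted log rate ratio cannot fall below √(2k/20). At an assumed k = 0.1 (a between-child coefficient of variation of √0.1, about 32%) that floor is 0.10, and power cannot exceed about 18% at any rate.

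**The case against.** Four points can be made for the plan.

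*Most clinical outcomes can be delivered.* A reader might infer that the whole clinical comparison fails. The documents do not support that: albuterol use, steroid courses, hospitalizations and the control score all have a stated source. The collection gap is confined to cough and wheeze.

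*The control score is not absent from the plan.* A reader might infer that it is collected and then ignored. Section 1.8 makes it a secondary endpoint, the synopsis promises a comparison between arms, and the continuous outcomes in 15.1 are given as examples only, so the mixed model could cover it. Section 15 also promises a detailed analysis plan. What stands is that the lists disagree and that no analysis of the score is named.

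*A symptom item may exist elsewhere.* Section 8 refers to a Schedule of Events in Appendix 1, which is not in the text reviewed, and 16.1 allows for other data from the visit. Neither shows that episodes are counted, and the detailed visit lists make it unlikely, but the sponsor should check the appendix.

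*The 94% is not only about cough and wheeze.* The wording is open-ended, and the count examples in 15.1 start with beta-agonist use, which the counter can document. This is correct. The figure could be restated for albuterol, but the missing rate and overdispersion matter equally there.

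**Conclusion.** The point holds in limited form. Cough and wheeze counts are declared, modelled and powered without any stated means of recording them, subject to Appendix 1. The 94% is unsupported: no rate or overdispersion is given, and under a pure Poisson model with 20 per arm it needs about 117 episodes per child in six weeks. At an assumed one episode a day power is about 56%, and about 32% with twofold overdispersion. It would go too far to call the 94% proven wrong, because a high enough rate with no overdispersion would give it; the documents simply do not state that rate. The event rates, the overdispersion values and the use of two-sided 0.05 for counts are assumptions.

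Separately, the control score is collected at both visits and promised as a comparison, but it is left out of 4.3 and the synopsis secondary-endpoint row and has no named analysis. The analysis of the lung-function primary endpoint is not affected by either gap.

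**What to change.** 1. Remove cough and wheeze episode counts, and their dichotomised versions, from section 1, 15.1, 15.2 and the matching synopsis rows. Editing the body alone would leave the synopsis in contradiction.
2. Withdraw the 94% figure, or restate it for albuterol use only, showing the assumed rate and overdispersion.
3. Use one secondary-endpoint list in 1.8, 4.3 and the synopsis, and include the asthma control score in it.
4. In 15.1, name the between-arm analysis of that score: the Visit 3 score by ANCOVA on arm and Visit 2 score.

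This costs wording only and needs no new data. The downside is the loss of a stated symptom-count outcome, which the listed procedures could not have produced. If the sponsor wants to keep it, the alternative is a defined instrument with a recall period, in place before enrolment. That adds data collection and would still need a power statement with its rate and overdispersion shown.
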